### 4.3.2.3 Predicted FEV1

Change from baseline in percentage predicted FEV1 will be analysed by means of an MMRM model as for the endpoint "Percentage predicted FEV1".

### 4.3.2.4 Asthma symptoms

The average asthma DSS, the average asthma VAS and the average daily dose of SABA use over the 2-week diary assessment (before V5, V6, V7, V8, V9, V10 and V11) will be analysed by means a MMRM. The analysis includes a square root transformation of the response variable, treatment, visit, and treatment-by-visit interaction, age group (<12 years/≥ 12 years) and region as fixed effects and a square root transformation of the baseline score as a covariate. Different residual errors for each treatment group will be specified and the within-subject correlated errors are modelled by an unstructured covariance.

For each visit and for the overall treatment effect across all visits, the between treatment comparison will be performed by means of a t-test with Kenward-Roger degrees of freedom approximation. The resulting p-value will be reported together with the difference in back-transformed adjusted means, calculated based on a second-order Taylor series expansion. As additional information the relative difference of the back-transformed adjusted means is reported together with 95% confidence limits. The latter is calculated based on Fieller's theorem (Fieller 1954).

The global evaluation of allergic asthma as binary outcomes "improved/not improved" will be analysed using a GLMM with a logit link function, treatment, age group (<12 years/≥ 12 years) and region as fixed effects. From the GLMM model, the odds ratio for having an improved outcome of active treatment relative to placebo will be presented together with the coherent p-values and 95% confidence limits. Additionally, Fishers exact test will be applied to the binary response of the global evaluation.

The ACQ/ACQ-IA (see section **7.1.1.5**) will also be analysed by means of a MMRM model as for the average asthma DSS, asthma VAS and the average daily dose of SABA, but without a square root transformation of the data.
Type of document	Date:	11-Aug-2022	
Document ID	Version:	4.0	
	Status:	Final	
INTERNAL USE	Page:	36 of 79	

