11.23.7 Global evaluation

At the final visit the subjects will be asked about their perception of the treatment efficacy during the treatment period answering the following question:

Rhinitis

"Compared to your rhinitis symptoms before starting treatment with the IMP, how are you feeling overall now?"

- 1. Much better
- 2. Better
- 3. The same
- 4. Worse
- 5. Much worse

Asthma

"Compared to your asthma before starting treatment with the IMP, how are you feeling overall now?"

- 1. Much better
- 2. Better
- 3. The same
- 4. Worse
- 5. Much worse

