The global evaluation as binary outcomes "improved/not improved" will be analysed using a generalised linear mixed model (GLMM) model.

In addition, all efficacy endpoints will be presented in summary tables.

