#### 4.3.2.5 Rhinitis symptoms and symptomatic medication

The average TCRS, the average rhinitis DSS, the average rhinitis DMS and the average rhinitis CSMS will be analysed using a similar MMRM model as described for the average asthma DSS and asthma VAS.

The global evaluation of allergic rhinitis will be analysed using a similar GLMM model as described for the global evaluation of allergic asthma.

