#### 7.1.1.8 Global evaluation of rhinitis and asthma

At the final visit the subjects will be asked about their perception of the treatment efficacy during the treatment period answering the following question regarding rhinitis: "Compared to your rhinitis symptoms before starting treatment with the IMP, how are you feeling overall now?".

Subjects will additionally be asked about their perception of the treatment efficacy during the treatment period answering the following question regarding asthma: "Compared to your asthma symptoms before starting treatment with the IMP, how are you feeling overall now?".

A subject answering "better" or "much better" will be categorised as "improved". A subject answering "much worse", "worse" or "the same" will be categorised as "not-improved".

Type of document	Date:	11-Aug-2022	
Document ID	Version:	4.0	
	Status:	Final	
INTERNAL USE	Page:	48 of 79	

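### Both global evaluations are recorded on five ordered categories but tested only as improved/not improved; adding a cumulative-logit analysis would be a cheap gain in sensitivity

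*SAP*

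**What the plan says.** Protocol 11.23.7 (Global evaluation) asks one question per condition at the final visit. For asthma it is "Compared to your asthma before starting treatment with the IMP, how are you feeling overall now". The rhinitis question is parallel. Both offer the same five ordered answers: much better, better, the same, worse, much worse.

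SAP 7.1.1.8 groups better and much better as improved, and the other three answers as not improved. SAP 4.3.2.4 then states: "The global evaluation of allergic asthma as binary outcomes 'improved/not improved' will be analysed using a GLMM with a logit link function", with treatment, age group and region as fixed effects and an odds ratio as the result. It adds: "Additionally, Fishers exact test will be applied to the binary response of the global evaluation". For rhinitis, SAP 4.3.2.5 says "The global evaluation of allergic rhinitis will be analysed using a similar GLMM model as described for the global evaluation of allergic asthma" and does not mention Fisher's test. The binary form was already in Protocol 15.8: "The global evaluation as binary outcomes 'improved/not improved' will be analysed using a generalised linear mixed model (GLMM) model".

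SAP 4.1 promises summary tables for all efficacy endpoints and frequency tables for categorical variables. It does not say that all five categories will be shown. Neither document gives a reason for the cut, an expected distribution of answers, or a power figure for these items.

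**The concern.** Two pieces of ordering that were collected are not used in any test. A child who moves from better to much better counts as unchanged, and so does one who moves from worse to the same. Neighbouring subject-reported endpoints in SAP 4.3.2.4 (asthma symptom score, asthma VAS, ACQ) are analysed on their full scales.

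The loss is largest when most placebo subjects already answer better or much better. That is conceivable here: subjects enter with recent exacerbations and current symptoms, stay on controller treatment with rescue medication supplied, and are asked after about two years. The documents give no data on this, so it is an assumption. What is at stake is the sensitivity of two supportive endpoints, not the validity of any test.

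**Working it through.** **The plan's own figure.** There is none for the global evaluations. The only sample-size figures concern the primary endpoint (Protocol 15.1, SAP 5). Its formula gives 203.1 per arm against the printed 202 (negative binomial, 30% reduction, 86 weeks) and 207.0 against 205 (Poisson, 20% reduction). Allowing for drop-out, 205/0.7 = 293, in line with about 300 per arm. Only the 30% drop-out is carried over here.

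**Inputs from the documents**
- 533 randomised (SAP 1.2). Nine subjects at site 613 contribute no efficacy data (SAP 3.1), which leaves 524, or 262 per arm.
- With 30% drop-out, 262 × 0.7 = 183 per arm.
- Two-sided 5% level (SAP 4.1).

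**Inputs assumed**
- Five placebo splits (much better/better/same/worse/much worse, %), and a common odds ratio (OR) of 1.4 or 1.6 applied at every cut.

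**Formulas**
- Active arm: each cumulative placebo proportion c becomes c·OR/(1 − c + c·OR).
- Binary test, n per arm, p0 and p1 improved, mean m: power = Φ{[|p1 − p0|√n − 1.96√(2m(1 − m))] / √(p0(1 − p0) + p1(1 − p1))}.
- Five-category proportional-odds test (Whitehead): V = (2n/12)(1 − Σ p̄³), where p̄ is the mean proportion in each category; power = Φ(log(OR)·√V − 1.96).

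**One case in full:** split 35/40/20/4/1, OR 1.6, n = 183.
- Cumulative placebo 0.35, 0.75, 0.95, 0.99 becomes 0.463, 0.828, 0.968, 0.994.
- Binary: 75.0% against 82.8% improved; power 44.3%.
- Ordinal: Σ p̄³ = 0.128; V = 30.5 × 0.872 = 26.6; 0.470 × 5.158 − 1.96 = 0.464; power 67.9%.
- Gain: about 23.5 points.

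**All settings at 183 per arm** (binary / ordinal power %, gain in points)

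| Placebo split | Improved | OR 1.4 | OR 1.6 |
|---|---|---|---|
| 10/35/40/12/3 | 45% | 36.1 / 41.8, 5.7 | 61.0 / 68.8, 7.8 |
| 15/35/45/4/1 | 50% | 35.9 / 41.2, 5.3 | 60.4 / 68.1, 7.7 |
| 20/40/30/8/2 | 60% | 33.8 / 42.1, 8.4 | 56.7 / 69.1, 12.4 |
| 35/40/20/4/1 | 75% | 26.4 / 41.3, 14.8 | 44.3 / 67.9, 23.5 |
| 40/40/17/2/1 | 80% | 22.9 / 40.4, 17.5 | 38.2 / 66.7, 28.4 |

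The gain at 183 per arm is thus 5.3 to 28.4 points. Simulating the same settings puts the low end nearer 4. At 262 per arm the formulas give 6.5 to 30.5.

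**Other splits.** With the OR set so that the ordinal test has 80% power at 183 per arm, a split of 5/45/45/4/1 gives a gain of 4.4 points and 45/40/13/1.5/0.5 gives 39.4. The range therefore depends heavily on where placebo answers fall.

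**Fisher's test.** In simulation at 183 per arm and OR 1.7, power for ordinal / chi-square / Fisher was 80/68/65% (20/35/30/10/5), 78/59/54% (30/40/25/4/1) and 78/73/69% (10/35/45/8/2). Fisher costs about 4 further points against chi-square.

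**Effects at one boundary only** (simulation, split 35/40/20/4/1, 8 points moved)

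| Move | n per arm | Binary | Ordinal |
|---|---|---|---|
| Same to better | 183 | 47% | 13–14% |
| Same to better | 262 | 61–62% | 18% |
| Better to much better | 183 | 5% | 19% |
| Better to much better | 262 | 5% | 24% |

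**The case against.** The case for leaving the plan alone is substantial. The binary analysis is valid, was fixed in the protocol, cuts at the neutral answer, and yields an odds ratio that is easy to read. No guideline is needed to justify that for an additional secondary endpoint. The items have no estimand (SAP 1.1.9) and lie outside the hierarchy (SAP 2.1), and the trial was not sized for them. All of this stands, and it is why the point is optional.

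A reader might infer three stronger things that the documents do not support:

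- **That the binary cut generally loses power.** Every split and odds ratio above is assumed, and the sign changes with the shape of the effect. For the one-boundary cases at 183 per arm, the binary test leads by about 33 points in one direction and the ordinal test by about 14 in the other.
- **That the ordinal model should replace the responder analysis.** The same comparison argues against this: if benefit lies only at same-to-better, the ordinal model would lose more than it could gain in the opposite case.
- **That graded subject-reported benefit is lost.** Asthma and rhinoconjunctivitis VAS, symptom scores and ACQ keep their full scales over visits 5 to 11.

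The 262 per arm figure is also optimistic. The item is asked once, at the final visit, and SAP 4.3 uses no secondary-endpoint data collected after treatment discontinuation. It would need an on-treatment answer from every subject in the full analysis set.

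What survives is narrower: the collected ordering enters no planned test, and an added analysis would use it.

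**Conclusion.** The point holds as a low-cost improvement. Every planned test of both global evaluations uses only the improved/not improved cut; Fisher's test is explicit for asthma alone. Under a roughly proportional shift, with 45% to 80% of placebo subjects improved, OR 1.4 to 1.6 and 183 per arm, a five-category test gains about 5 to 28 points of power, rising to about 30 at 262 per arm. The 183 itself rests on the planning drop-out, not on observed completion. The calculations omit age group and region. The gain is not guaranteed, since an effect confined to same-to-better favours the binary test clearly. For that reason the two analyses belong side by side. No inference in the test hierarchy changes.

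**What to change.** In SAP 4.3.2.4 and 4.3.2.5:

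- Keep the improved/not improved logit model and its odds ratio as prespecified.
- For each global evaluation, add a proportional-odds (cumulative logit) model on the five categories with treatment, age group and region. Report the common odds ratio with its 95% confidence interval.
- Tabulate the five-category distribution by arm, so that a shift confined to one boundary is visible.
- Let the ordinal model take the place of the unadjusted Fisher test, which repeats the same cut with a second p-value.
- Record the change in SAP 4.8 before unblinding. If unblinding has already taken place, Protocol 15 requires the analysis to be marked as post hoc.

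The cost is some SAP wording and one more model per item on data already collected, with no burden on subjects. The downside is one more analysis and a proportional-odds assumption on an endpoint outside multiplicity control. The retained responder odds ratio covers the case in which that assumption fails at same-to-better.

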#### 4.3.2.5 Rhinitis symptoms and symptomatic medication

The average TCRS, the average rhinitis DSS, the average rhinitis DMS and the average rhinitis CSMS will be analysed using a similar MMRM model as described for the average asthma DSS and asthma VAS.

The global evaluation of allergic rhinitis will be analysed using a similar GLMM model as described for the global evaluation of allergic asthma.

#### 4.3.2.6 Rhinoconjunctivitis symptoms and symptomatic medication

The average total rhinoconjunctivitis TCS, the average rhinoconjunctivitis DSS, the average rhinoconjunctivitis DMS, the average rhinoconjunctivitis CSMS and the average rhinoconjunctivitis VAS will be analysed using a similar MMRM model as described for the average asthma DSS.

#### 4.3.2.7 Immunology

Summary tables by treatment group and visit will be produced for raw data and  $log_{10}$ -transformed data of specific IgE and IgG4 and for raw data of IgE-BF against *D. pteronyssinus* and *D. farinae* by visit. Also, the change from baseline in the immunological data (IgE, IgG4, IgE-BF, log10(IgE) and  $log_{10}(IgG_4)$ ) will be summarised.

Change from baseline in log10(IgE) and log10(IgG4) (against *D. pteronyssinus* and *D. farinae*) at visit 7 and 11 will be analysed using a MMRM model. For IgE and IgG4, change from baseline of the log10-transformed immunological parameter is the response variable. Treatment, visit and treatment-by-visit interaction will be included as fixed effects, the log10-transformed immunological parameter at baseline is a covariate. Different residual errors for each treatment group will be specified in the MMRM model. The correlation structure of the repeated measure is an unstructured covariance. The active dose group will be compared to placebo at each visit using a t-test in the MMRM model and an overall treatment ratio across all visits will be estimated together with a p-value based on the MMRM model. The corresponding difference in adjusted means reported on the log10 scale, will be calculated together with the associated p-value and 95% confidence intervals.

Change from baseline in IgE-BF will be analysed using a similar MMRM model as described for specific IgE and IgG4. However, IgE-BF data will not be  $log_{10}$ -transformed.

The estimated mean change from baseline in the immunological parameters ( $log_{10}(lgE)$ ,  $log_{10}(lgG4)$ ) and lgE-BF with 95% confidence limits will be plotted by time (visit) and treatment.

If IgE values are recorded as "0" or "<0.70" the value 0.69 will be used. If the value is recorded as ">800", 801 will be used. If  $IgG_4$  values are recorded as "<0.15" the value 0.14 will be used. If the value is recorded as ">30", 31 will be used. Otherwise, data are used as measured.

Additional analyses are performed for all immunology endpoints using the above-described models, but where the age-group is divided into sub-age-groups: 5-7 years, 8-11 years and at least 12 years. Estimates are presented by sub-age-group.

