### 1.2.3 Randomisation

The randomisation list has been generated by a trial-independent statistician and will not be accessible to trial personnel involved in the conduct of the trial, until the database has been locked.

At least 45% of the subjects will be 5-11 years of age at the time of randomisation in accordance with the recommendation of EMA/PDCO standard paediatric investigation plan for allergen products for specific immunotherapy **(EMA and PDCO 2015)**. No other stratification will be used in this trial.

When a subject is randomised, a unique number is assigned for the first dispensing of IMP.

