#### Statistical models

- The model for the key secondary endpoints "proportion of days with nocturnal awakening which require SABA" is changed from a generalized linear mixed effect model to a marginal logistic regression model estimated by a GEE approach. GEE estimation has fewer model assumptions and hence reduces the risk of wrong model assumption. In addition, the treatment effect has an interpretation as a population average estimate in the GEE approach.
- All MMRM analyses have been aligned and updated to include the following fixed factors: treatment, visit, treatment-by-visit interaction, age group and region. Baseline values at visit

Type of document	Date:	11-Aug-2022	
Document ID	Version:	4.0	
	Status:	Final	
INTERNAL USE	Page:	42 of 79	

3 will be included as a covariate. The default within-subject correlation structure has been changed from a Toeplitz covariance to an unstructured covariance.

The model for the 2 additional secondary endpoints "Time to first severe asthma exacerbation" and "Time to first clinically relevant asthma exacerbation" has been changed to a Cox proportional hazards regression analysis including treatment and age group (<12 years/≥ 12 years) as effects. Region is included as a random effect assumed to follow a gamma distribution.

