#### 7.2.3 Secondary endpoints analysis

In the analysis of the first and second key secondary endpoints, the marginal model will be estimated using a GEE- approach. The treatment effect on the logit scale is an average treatment effect across all visits and will be estimated as a contrast of parameters in the marginal model. The corresponding odds ratio for proportions of days with nocturnal awakening requiring SABA of active treatment relative to placebo will be presented together with the coherent p-value and 95% confidence limit. If convergence issues are encountered for the marginal logistic regression model, other working covariance structures will be considered (e.g. an independence structure (IND)).

In the analysis of the third key secondary endpoint and the additional secondary endpoints, the treatment effect is the average of the treatment effect across all visits and will be estimated as a contrast of the parameter estimates in the MMRM model. The corresponding p-value will be calculated by means of a t-test with Kenward-Roger degrees of freedom approximation. LSMeans by treatment group will be displayed. In addition, the relative difference will be reported together with 95% confidence limits calculated based on Fieller's theorem for non-transformed data. In models where data is square-root transformed, the absolute difference will be calculated based on a second-order Taylor series expansion.

If an MMRM model with an unstructured covariance matrix fails to converge, unstructured correlations (UNR), Toeplitz (Toep) or compound symmetry (CS) will be used instead, prioritized in the listed order. If the MMRM model still fails to converge, a reduced model is used to estimate starting values for the type of covariance structure mentioned above. If the use of starting values will still not lead to convergence, the model is reduced by eliminating effects backwards (i.e. first region then age group).

If a Cox proportional hazards regression models fails to converge in the analysis of time to events, e.g. due to few events, then Firth's penalized maximum likelihood estimation is used.

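### The immunology MMRM in SAP 4.3.2.7 omits age group and region, contrary to SAP 4.8 and 7.2.3, and the method for its sub-age-group estimates is not stated

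*SAP*

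**What the plan says.** SAP 4.3.2.7 writes out the MMRM for change from baseline in log10 IgE and log10 IgG4 at visits 7 and 11. On the mean model it says "Treatment, visit and treatment-by-visit interaction will be included as fixed effects", and that the log10-transformed "immunological parameter at baseline is a covariate". No other term is named. IgE-BF follows the same route without the transformation: "Change from baseline in IgE-BF will be analysed using a similar MMRM model as described for specific IgE and IgG 4".

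The section ends by planning additional analyses of all immunology endpoints with the "above-described models, but where the age-group is divided into sub-age-groups: 5-7 years, 8-11 years and at least 12 years". Estimates are to be shown for each of these bands.

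Two other places in the SAP describe the MMRMs differently:

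- SAP 4.8, under Statistical models: "All MMRM analyses have been aligned and updated to include the following fixed factors: treatment, visit, treatment-by-visit interaction, age group and region".
- SAP 7.2.3 opens its MMRM rules with "In the analysis of the third key secondary endpoint and the additional secondary endpoints". As the last resort when an MMRM does not converge, "the model is reduced by eliminating effects backwards (i.e. first region then age group" in that order.

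On randomisation, SAP 1.2.3 gives a minimum share of 5-11-year-olds and then says "No other stratification will be used in this trial".

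**The concern.** Two programmers working from this SAP could fit different main models to the same immunology data: one following 4.3.2.7 literally, the other following 4.8. Age group is also the apparent randomisation stratum, so one would expect to see it in the model.

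The by-band analysis is more open. It tells the analyst to divide a term that the described model does not have. The most literal repair is to insert a three-level age factor where a two-level one was meant to be. That changes the adjustment but gives no band-specific treatment effect. A table of treatment differences built that way would show perfect agreement across ages whatever the data were.

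The age comparison has some substance. Protocol 1.2 and 3.3 use one dose from 5 years of age upward, independent of age and body weight. A by-age look at the immunological response is therefore informative, and how it is obtained should be fixed before unblinding.

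**Working it through.** The plan gives no figure on this point to reproduce. The check has three parts.

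**1. Which terms does each section put in the MMRM?**

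| SAP section | Endpoint | Age group | Region |
|---|---|---|---|
| 4.3.1.3 | percentage predicted FEV1 | yes | yes |
| 4.3.2.4 | asthma symptom score, asthma VAS, SABA dose | yes | yes |
| 4.3.2.7 | IgE, IgG4, IgE-BF | no | no |
| 4.8 | all MMRMs | yes | yes |
| 7.2.3 | FEV1 and additional secondary endpoints | presupposed | presupposed |

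Immunology is listed among the additional secondary endpoints in SAP 1.1.7 and in Table 3, so 7.2.3 applies to it. A rule that removes region and then age group has nothing to remove from the model in 4.3.2.7. The sentence in 4.8 sits in a list of changes from the protocol, but it describes the models as they now stand, so it is not superseded text.

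**2. What can each version of the model estimate by age band?**

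Write the mean for treatment t, visit v, age band a and baseline b as

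E(y) = m + A(t) + V(v) + AV(t,v) + G(a) + c·b.

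The active-minus-placebo difference at visit v in band a is

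[A(act) − A(pbo)] + [AV(act,v) − AV(pbo,v)].

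G(a) cancels, so the difference does not depend on a. Leaving G(a) out, as 4.3.2.7 does, gives the same result for a single pooled fit. A difference by band needs a term AG(t,a), or a separate fit of the model within each band.

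**3. Illustration on simulated data.**

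All inputs are assumptions except the number of subjects, 76 + 249 + 199 = 524, from Protocol Table 14. The assumptions are: two visits; band shares of 20%, 30% and 50%; true log10 treatment differences of 0.3, 0.5 and 0.7; normal baseline (SD 0.5, slope −0.2); subject SD 0.3; residual SD 0.2. The mean model was fitted by ordinary least squares. That is enough here, because the cancellation in part 2 comes from the mean model and not from the covariance structure. Treatment difference averaged over both visits:

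| Model | 5-7 y | 8-11 y | 12+ y |
|---|---|---|---|
| as written, one pooled fit | 0.534 | 0.534 | 0.534 |
| plus three-level age main effect | 0.534 | 0.534 | 0.534 |
| plus treatment-by-age terms | 0.389 | 0.397 | 0.686 |
| as written, fitted within each band | 0.400 | 0.397 | 0.689 |

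The common value is close to the share-weighted mean of the assumed effects, 0.2×0.3 + 0.3×0.5 + 0.5×0.7 = 0.56. As ratios, the main-effect version gives 10^0.534 = 3.4 in every band. The interaction version gives 10^0.389 = 2.4, 10^0.397 = 2.5 and 10^0.686 = 4.9. This is a single simulated dataset, so the band estimates differ from the assumed effects by sampling error. The interaction model in the third row also let the effects vary by visit, which is more than the fix below needs.

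**The case against.** The strongest reply is that the by-band analysis is feasible as written. A reader might infer that the described model cannot produce estimates by sub-age-group at all, or that the output is bound to show no age difference. The documents do not support either reading. Fitting the written model separately in each band satisfies the wording, and the last row of the second table shows that it recovers the pattern. The SAP nowhere says that the three-level factor is a main effect only, so the forced equality belongs to one possible implementation. Nor does 4.3.2.7 say that the estimates are treatment differences; adjusted means by arm would differ between bands even under a main-effect model. All of this stands. What remains is an unstated method.

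On the main model, the sponsor can say that the intended terms are recoverable: 4.8 and 7.2.3 agree, and the reference in 4.3.2.7 to dividing the age group suggests that its author thought the term was there. That makes a dropped phrase the likely cause, but it does not remove the conflict. A narrower reading would confine 4.8 to MMRMs already in the protocol, since Protocol 15.8 gives no immunology model. The word all in 4.8 and the scope of 7.2.3 weigh against it.

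Three further limits are fair:

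- The text on age in SAP 1.2.3 and Protocol 6.2 could describe a recruitment quota as well as a stratum.
- Region is not in every other model; the recurrent-event model in SAP 4.3.2.2 has only treatment and age group.
- A reader might infer that this is the only planned biomarker evidence by age. That cannot be verified, because the exploratory endpoints and their analyses are blacked out.

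**Conclusion.** The point holds in two parts. First, SAP 4.3.2.7 gives an immunology MMRM without age group and region, in conflict with 4.8 and with the fallback in 7.2.3. Second, the sub-age-group analysis refers to a term that this model lacks and does not say whether its estimates come from an interaction or from separate fits. One open reading, a main effect only, would make the treatment difference equal across bands whatever the data show.

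The size is modest. These endpoints lie outside the hierarchy in SAP 2.1 and have no estimand (SAP 1.1.9), so no primary or key secondary conclusion is affected. Baseline is already a covariate, so the precision gained from the two extra factors is probably small; the documents give no variance from which to calculate it. The 0.3, 0.5 and 0.7 effects are assumptions chosen to show the mechanism and do not predict trial results.

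**What to change.** In SAP 4.3.2.7:

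1. Add age group (<12/≥12 years) and region as fixed effects to the IgE, IgG4 and IgE-BF MMRMs, as 4.8 already says.
2. For the additional analysis, choose one method and state it. Either replace age group with the three-level factor and add a treatment-by-sub-age-group interaction, following the pattern of SAP 4.6.2 for the primary endpoint, or fit the model separately in each sub-age-group.
3. Say that the treatment contrast with its confidence interval is reported for each band.

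A three-way interaction with visit is optional and goes beyond what 4.6.2 does.

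The cost is a few sentences and a changed model statement, using data already collected. With two post-baseline visits, the written mean model has 5 coefficients (intercept, treatment, visit, treatment-by-visit, baseline). Age group adds 1 and the three-level region adds 2, giving 8. In the additional analysis the three-level age factor takes 2 in place of 1, and its interaction with treatment takes 2 more, giving 11. The price is that intervals in the 5-7 year band may be wide, and the table should be labelled descriptive.
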